317 schizophrenia, and indicate that empirical studies examining the efficacy of modulating VLPFC
318 functioning on paranoia are warranted.

319 To begin to address this gap, our preliminary work tested the efficacy of single-session
320 tDCS to VLPFC among undergraduate students with heightened subclinical paranoia. While
321 preliminary, we found a significant reduction in paranoid ideation after active stimulation but not
322 sham stimulation (Springfield, Isa, et al., 2021). Combined with previous work reporting that
323 regions of VLPFC demonstrated increased functional connectivity with amygdala in paranoid
324 patients compared with non-paranoid patients (Fan et al., 2021), our pilot tDCS study indicates
325 that VLPFC may be a potentially important treatment target for clinical levels of paranoia in
326 patients with SSD. As such, using tDCS to impact functioning of VLPFC not only offers
327 perspective regarding the neurobiological mechanisms of paranoid ideation by providing
328 evidence of a causal link between VLPFC activity and the experience of paranoia, but also holds
329 important implications for treating clinical levels of paranoia in patients with SSD.
330

331 **3. Project Outline, Goals, and Hypotheses**

332 To address these issues, the current research aimed to investigate the effects of tDCS on
333 paranoid ideation and social functioning in individuals with SSD. Individuals who met
334 diagnostic criteria for schizophrenia or schizoaffective disorder, demonstrated clinically
335 significant levels of recent paranoia, and had no contraindications for neural stimulation (e.g.,
336 presence or history of epilepsy or seizures) were recruited. Our proposed mechanistic model
337 suggests that either decreasing activation of the amygdala or increasing activation of prefrontal
338 regulatory regions (e.g., VLPFC) may reduce paranoia. However, given the amygdala's
339 subcortical location, VLPFC was targeted in the present study as it is more feasibly modulated
340 via tDCS. A double-blind, crossover design was used to administer both active and sham
341 stimulation conditions to each participant to allow within-subject comparisons. The most widely
342 adopted and commonly used parameters were utilized during active stimulation to ensure safety
343 and efficacy (i.e., 2mA, 20min) (Brunoni et al., 2014; Gupta et al., 2018). To increase potential

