456 maintained the list containing the condition information corresponding to each visit during the
457 study in case the blind conditions needed to be revealed in real time (e.g., if participants reported
458 adverse effects during tDCS).

459 *6.3 Stimulation Parameters*

The total stimulation time of 40 minutes was divided into two twenty-minute sessions to allow repeated stimulation, which may increase efficacy (Cheng et al., 2020; Kim et al., 2019). The active stimulation included active current at 2mA, ramping up over 15 seconds, sustaining for 20 minutes, and finally ramping down for 15 seconds. The dimensions of each electrode were 5 × 7 centimeters in size (35 cm^2), which led to a current density of 0.5714 mA/cm². For the sham condition, electrodes were still attached for 20 minutes each session, but the actual stimulation time was limited to 45 seconds per session, with 15 seconds of gradual stimulation, leading up to 15 seconds of full stimulation, and finally 15 seconds of ramping down. This limited stimulation mimicked the ramp up phase of active stimulation, making it more difficult for participants to guess the condition. The machine also automatically performed impedance control checks throughout the neurostimulation to ensure that both the participant and the experimenter could not tell which condition was being administered. Following each session,

472 inquiries into the participants' perceptions of the suspected condition showed that their accuracy
473 in identifying the correct condition was below chance levels (47%), supporting the efficacy of
474 the blinding procedures.

475

476 **Figure 3. Computational simulation of tDCS-induced current density.** (A) shows the
477 montage location in the study (1 = right VLPFC, 2 = left VLPFC). (B) reveals the distribution of
478 the current density estimated based on the stimulation location and parameters.

479

480 6.4 Current Modeling

481 To better characterize the current distribution during the stimulation, current modelling
482 was conducted for the active condition. This computational simulation utilized a finite element
483 model derived from MRI, implemented through the Comets toolbox (Jung et al., 2013) in Matlab
484 (<http://www.COMETStool.com>). **Figure 3** illustrates a detailed three-dimensional (3D)
485 numerical analysis of the current density generated by tDCS based on the montage applied in this

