679 It is possible that participants may feel tired, fatigued or anxious during the research
680 procedure; however frequent breaks were built into the lab portion of the study to reduce this
681 possibility. Additionally, participants were informed that they may take a break or terminate their
682 participation at any time. The most common side effect of tDCS neurostimulation is skin redness
683 just beneath the electrode. This effect usually wears off within one hour. Other potential risks
684 associated with tDCS include:

- 685 1. Itching at the electrode location; typically lasting less than an hour;
- 686 2. A small percentage of participants may experience mild dizziness upon stimulation onset.
687 After stimulation, this only lasts a few seconds and has no effect on balance;
- 688 3. Occasionally, temporary skin damage may occur beneath the electrode. This results in a week-
689 long darkening of the skin. At the planned current, the size of these marks, should they occur, is
690 only a few millimeters, posing a low risk;
- 691 4. After neurostimulation and the waiting period, participants may feel drowsy, but this effect
692 dissipates within one hour.

693 Finally, whenever information is gathered, there is a potential risk of loss of
694 confidentiality. This cannot be guaranteed, but every effort has been done to protect the privacy
695 of participants' information. Participants were assigned a random number that was used to
696 identify their data, and the file linking the number to the participants' email addresses and
697 birthdates was stored separately from the data they provide. This file will be erased upon
698 completion of the study. All data is stored in locked filing cabinets in secure offices at UTD, as
699 well as on password-protected/encrypted computers at UTD, and only study personnel who have
700 received extensive training in methods to protect confidentiality have access to the data.

701 *11.2 Potential Benefits*

702 It is possible that neurostimulation may reduce paranoid ideation and/or improve social
703 functioning for participants after active stimulation. However, the effects of tDCS are often
704 temporary, and we do not anticipate that such a short-term stimulation will have a lasting effect.
705 If this study is effective, subsequent research can investigate the ideal frequency and duration of
706 neurostimulation to deliver direct, long-lasting benefits.

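### Does the tenfold disagreement between current, electrode area and current density in Section 6.3 call for a change to the plan?

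*Combined protocol and SAP*

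**What the plan says.** Three stimulation figures stand together in Section 6.3 (Stimulation Parameters):

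- Current: "The active stimulation included active current at 2mA", held for 20 minutes in each of two sessions.
- Electrode size: "The dimensions of each electrode were 5 × 7 centimeters in size (35 cm^2").
- Density, presented as the consequence of the other two: "which led to a current density of 0.5714 mA/cm²".

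The current also appears in Section 3, where the parameters are said to have been chosen for safety "and efficacy (i.e., 2mA, 20min"). Section 6.4 and the caption of Figure 3 describe a computer model of the current distribution, but their text gives no numerical density. Section 11.1, on skin marks under the electrode, ties the risk to the current: "At the planned current, the size of these marks, should they occur, is" a few millimetres. No other section gives an electrode area or a current density for this study.

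**The concern.** Active against sham tDCS is the only comparison in this trial, and Section 6.3 is where the intensity of the active condition is defined. The density there is offered as the result of dividing the current by the area, and it is not that result. A reader who compares or reproduces the stimulation by density would be out by a factor of 10 if the printed current and area hold. A factor of 10 in an intensity figure also raises the question of whether a different current or a smaller electrode was used, and whether the current model in Section 6.4 was run with the wrong value.

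**Working it through.** **Inputs** (Section 6.3; the current is repeated in Section 3): current 2 mA; electrode 5 cm × 7 cm; printed density 0.5714 mA/cm².

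**Step 1, area.** 5 × 7 = 35 cm². This agrees with the printed area.

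**Step 2, density.** Current / area = 2 mA / 35 cm² = 0.05714 mA/cm². The printed figure is not reproduced. Ratio: 0.5714 / 0.05714 = 10.0.

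**Step 3, other readings in mA/cm².**

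| Reading | Calculation | Result |
|---|---|---|
| Both electrodes pooled | 2 / 70 | 0.0286 |
| Currents of the two sessions added | 4 / 35 | 0.114 |
| Lower end of the range cited from earlier studies (Section 2.5.1) | 1 / 35 | 0.0286 |
| Upper end of that range | 3 / 35 | 0.0857 |

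None gives 0.5714. The first two are not natural readings in any case: the area is stated for each electrode, and the two sessions are at least 3 hours apart (Section 3).

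**Step 4, what the printed density would need.** At 35 cm², a current of 0.5714 × 35 = 20.0 mA. At 2 mA, an area of 2 / 0.5714 = 3.50 cm². Neither value appears in the documents. They measure the size of the gap and are not evidence of what was done.

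**Step 5, units.** 2 mA = 0.002 A and 35 cm² = 0.0035 m², so 0.002 / 0.0035 = 0.5714 A/m². These are the four printed digits. Since 1 mA/cm² = 10 A/m², an A/m² figure labelled mA/cm² is overstated by exactly 10, which is the gap in Step 2. A misplaced decimal point would produce the same gap.

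**Step 6, where the density is used.**

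- Sample size (Section 4.1): built on Cohen's d = 0.51 from the pilot, α = .05, power 0.80 and a correlation of 0.3. No density enters.
- Randomization and sham (Sections 6.1 to 6.3): electrodes are placed identically in both conditions, and sham differs in stimulation time (45 seconds per session). The contrast is active against sham, whatever density is printed.
- Outcomes (Sections 7 and 8): questionnaires, tasks and EMA items. None depends on density.
- Analyses (Section 9): repeated-measures ANOVA, paired t-tests and multilevel models, with condition as a category. Density is not a covariate, a dose variable or a threshold.
- Risk (Section 11.1): refers to the current.
- Current model (Section 6.4): the text does not say which values were entered.

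**The case for a change.** The best argument for acting is that the error lies in the specification of the only intervention, can be shown from one paragraph without any outside source, and costs one line to correct. The conversion to text does not readily explain it either: the sentences and digits are intact, and turning A/m² into mA/cm² would require added characters. The current model in Section 6.4 is a place where a wrong value could have travelled.

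Most of this stands as a description. The figures do conflict, and a reader who takes only the density from Section 6.3 is misled by a factor of 10. Two parts are weaker. First, both inputs are printed beside the density, so a reader can redo the division and see the conflict at once. Second, nothing shows that the model used the printed density. Figure 3 is not visible in the text available, so any scale or unit on it could not be checked; it would in any case show a modelled distribution, not the quotient of current and electrode area.

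A small caution applies to the source text. The paragraph in Section 6.3 has lost its line numbers, and the squared unit is written in two different ways within one sentence. That is a reason to look at the PDF before correcting anything, but it does not remove the discrepancy.

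**Conclusion.** The disagreement is real and its size is a factor of 10: 0.0571 mA/cm² from the printed current and area, against 0.5714 mA/cm² as printed. It is best treated as a clerical slip that leaves the plan unchanged. The density is a derived, descriptive figure. Replacing it would not alter the number of participants, the randomization, the outcomes, the α of 0.05, any test or any estimate. The document reports the trial in the past tense, with 50 participants having completed it, so a text correction could not affect what was delivered.

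This rests on two assumptions. The first is that no decision in the trial was keyed to the printed density; no section shows one. The second is that the slip is one of notation. The match with 0.5714 A/m² supports this and the documents do not contradict it, but they do not confirm it either. This review does not say which of current, area, density or unit label is right. The three values in Section 6.3 must be reconciled with the device and electrode records, which is an editorial correction with no statistical consequence.

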344 efficacy, 2 sessions of stimulation were administered with a time interval of ≥ 3 hours (Bose et al.,
345 2014; Brunelin et al., 2012) for each condition. We utilized a higher frequency here compared
346 with our pilot study (Springfield, Isa, et al., 2021) because the alleviation of clinical levels of
347 paranoia may require multiple sessions of stimulation (Cheng et al., 2020; Selvaraj et al., 2021),
348 which may increase efficacy as suggested by previous research (Cheng et al., 2020; Kim et al.,
349 2019). Offline stimulations were employed because there are no tasks that can be used to train
350 the neural networks related to paranoid ideation (i.e., online stimulation) and previous literature
351 indicates that cognitive activity during tDCS may attenuate or even abolish the stimulation
352 effects (Horvath et al., 2014). Finally, in addition to measuring improvements in paranoia and

353 social functioning in the lab setting, we also administered short daily surveys to participants
354 multiple times per day for 7 days before and after the 1st stimulation session, as well as after the
355 2nd stimulation session. These ecological momentary assessments (EMA) allow for capturing
356 baseline paranoia severity as well as any delayed effects of neural stimulation in the real world.
357

357 3.1 Aims and Hypotheses

358 The specific goals and hypotheses of this project are listed below:

359 **Goal 1:** To examine whether applying tDCS to VLPFC will reduce paranoid symptoms in SSD.

360 *Hypothesis 1a:* Patients with SSD will show reduced paranoia symptoms after the active VLPFC
361 stimulation condition relative to sham stimulation as measured by *in-lab assessments* (i.e.,
362 decreased self-report paranoia, less attributional bias and hostility, more trust to strangers).

363 *Hypothesis 1b:* Patients with SSD will show reduced paranoia symptoms after the active VLPFC
364 stimulation condition relative to sham stimulation as measured by *EMA assessments* (i.e.,
365 reduced feelings of paranoia in daily life).

366 **Goal 2:** To examine whether applying tDCS to VLPFC will improve social functioning in SSD.

367 *Hypothesis 2a:* Patients with SSD will show better social performance after the active VLPFC
368 stimulation condition relative to sham stimulation as measured by *in-lab assessments* (i.e.,
369 improved self-report of social functioning).

370 *Hypothesis 2b:* Patients with SSD will show better social functioning after the active VLPFC

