618 along a 7-point scale, as well as the emotions associated with and perceptions of social
619 interactions since the last survey (e.g., did you interact with anyone since your last survey?).
620 Affective states since the past alarm were rated on a 7-point scale using the following items:
621 sad/depressed, excited, irritated, happy, belongingness, and burden to others. Expectations

622 regarding subsequent interpersonal situations were also rated on a 7-point scale (e.g., how much
623 interest do you have in interacting with people for the rest of the day?). **Appendix B** contains the
624 complete list of EMA questions (i.e., paranoia: Q1; social functioning: Q3, Q4, Q5, Q6, Q7, Q14,
625 Q15). Adherence was monitored remotely via a secure platform, and participants who missed 3
626 consecutive surveys were contacted by research personnel to identify and resolve any issues.
627 Compensation of the EMA periods was determined by the actual number of surveys completed
628 to encourage adherence.

629 A total of 47 (out of 50) participants had full data across three EMA periods. One
630 participant did not have a phone and chose not to participate in the EMA protocol. Two
631 participants completed baseline EMA but lost their phones afterwards, and thus chose not to
632 complete the two remaining EMA periods. EMA compliance in the current study was above 80%
633 across the three periods (EMA1 = 82.74%, EMA2 = 83.38%, EMA3 = 80.04%).

634

635 **9. Statistical Analyses Plan**

636 For all tests, a conventional threshold of $\alpha = 0.05$ was used. While opting not to correct
637 for multiple comparisons may permit alpha inflation, we did not want to risk missing any
638 potential therapeutic effects in this treatment study by increasing the likelihood of Type II errors.
639 Therefore, in line with a large body of existing literature, findings that passed the significance
640 level of $\alpha = 0.05$ are presented.

641 **Hypothesis 1a:** To test the reduction in paranoia measured in the lab (active vs. sham
642 stimulation), repeated-measures ANOVAs were performed for self-reported state paranoia
643 measured both before and after the stimulation, while paired-samples t-tests were performed for
644 paranoia-related outcomes measured only after stimulation (i.e., attributional bias and hostility,
645 trust to strangers).

646 **Hypothesis 1b:** Multilevel modeling (MLM) with maximum likelihood robust estimation was

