647 used to test the differences in daily feelings of paranoia (i.e., Q1) across the three EMA periods
648 (EMA-baseline vs. EMA-active vs. EMA-sham), with the condition of the EMA period being
649 dummy-coded.

650 **Hypothesis 2a:** To test the improvement in social functioning measured in the lab (active vs.
651 sham stimulation), paired-samples t-tests were performed for self-reported social functioning
652 measured only after the stimulation.

653 **Hypothesis 2b:** MLM with maximum likelihood robust estimation was used to test the
654 differences in daily social functioning (i.e., Q3, Q4, Q5, Q6, Q7, Q14, Q15) across the three
655 EMA periods (EMA-baseline vs. EMA-active vs. EMA-sham), with the condition of the EMA
656 period being dummy-coded.

657 Notably, one of the daily social functioning questions (i.e., Q3: Since the past alarm, who
658 have you interacted with?) has a different score range. It is quantified as the frequency of social
659 interactions, where a higher score indicates more interactions across a broader range of people
660 categories (range = 0-5). In contrast, the remaining six items adhere to a score range of 1-7.
661 Therefore, we performed MLM separately for Q3 (named as social interaction frequency) and for
662 the average of items Q4, Q5, Q6, Q7, Q14, and Q15 (named as social interaction motivation and
663 experience) for parsimony.

664

665 **10. Participant Payment**

666 Participants were compensated \$20 for completing the enrollment visit, \$100 for each of
667 the two in-lab stimulation visits, and up to \$16 for each of the 7-day EMA periods (three EMA
668 periods in total), totaling a maximum of \$268. Participants who enrolled in the study but were
669 found ineligible during screening were still compensated \$20. If participants stopped taking part
670 in the study or were withdrawn by the research team, they received \$5 for each 20 minutes
671 completed during the lab visits. For example, if they completed 1 hour of the study, they were
672 paid \$15. Compensation for each EMA period was determined by the number of surveys
673 completed, with \$0.75 paid for each survey except for the final survey, which was worth \$1 (to
674 allow for an even amount of \$16 per EMA period if all 21 surveys were completed). Parking on
675 campus was provided for participants.
676

677 **11. Risk and Benefits Assessments**

678 *11.1 Potential Risks*

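### Section 9 does not make active minus sham the deciding EMA contrast for H1b and H2b, so a time-confounded comparison with the always-first baseline week could be read as support; no period term is stated

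*Combined protocol and SAP*

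**What the plan says.** Section 3.1 words both EMA hypotheses as a comparison of the active VLPFC "stimulation condition relative to sham stimulation as measured by" EMA. Section 9, under Hypothesis 1b, says multilevel modelling with robust maximum likelihood was "used to test the differences in daily feelings of paranoia (i.e., Q1) across the three EMA periods", the condition factor being "EMA-baseline vs. EMA-active vs. EMA-sham), with the condition of the EMA period being" dummy-coded. Hypothesis 2b has the same three levels and is fitted separately for social interaction frequency and for social interaction motivation and experience. In the same section, the paragraphs for H1a and H2a do name active versus sham as the comparison.

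Section 3 says surveys were sent "multiple times per day for 7 days before and after the 1st stimulation session, as well as after the" second, in order to capture "baseline paranoia severity as well as any delayed effects of neural stimulation in the real world". The baseline week therefore precedes stimulation visit 1 for everyone. Only active and sham were counterbalanced: 26 active first and 24 sham first (section 6.2). Section 8 reports: "A total of 47 (out of 50) participants had full data across three EMA periods". It does not give their split by sequence.

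Section 9 uses alpha 0.05 for all tests without multiplicity correction, and says that findings passing it are presented.

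**The concern.** The hypotheses concern one contrast, active minus sham. A dummy-coded three-level factor offers three pairwise comparisons and, if wanted, a joint test. Section 9 does not say which of these decides H1b or H2b.

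Two of the pairwise comparisons use baseline, which is not randomised in order and lies earlier in time. On the mean gaps in section 5, the week after visit 2 starts 7 + 14.58 = 21.6 days after baseline EMA starts if baseline EMA directly precedes visit 1. If baseline EMA starts at enrolment, the gap is 13.59 + 14.58 = 28.2 days. Habituation to the surveys, regression to the mean or a change in clinical state over those weeks would move both post-stimulation weeks away from baseline under active and sham alike. A coefficient against baseline could then be significant with no active-sham difference. Under the stated rule for presenting findings, nothing keeps it from appearing as support for H1b or H2b.

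**Working it through.** **Inputs.** From the documents: 47 EMA completers (section 8); sequences 26/24 (section 6.2); alpha 0.05 (section 9), taken as two-sided because sidedness is not stated; correlation 0.3, used in section 4.1 only for the ANOVA sample size. Assumed: drift d, a shift of both post-stimulation weeks from baseline that is equal under active and sham; a change π from the first to the second post-visit week; and a within-person correlation ρ of 0.3 up to 0.8. Shifts are in SD units of participant-by-period means, which are the unit of calculation.

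**1. The plan's own figure.** Section 4.1 gives n = 46. Reading its 0.25 (printed as β) as Cohen's f, with m = 2 measurements: λ = f²·n·m/(1 − ρ) = 0.0625 × 46 × 2/0.7 = 8.21 on (1, 45) df, giving power 0.801. So 46 reproduces, and it matches a two-level comparison; m = 3 would give 38. The figure concerns the planned ANOVAs. No power calculation is given for the EMA models.

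**2. Comparisons involving baseline, no treatment effect.** Period means are (0, −d, −d).
- Active or sham versus baseline: λ = N·d²/[2(1 − ρ)], df (1, 46). At d = 0.2, ρ = 0.3: 47 × 0.04/1.4 = 1.343.
- Joint three-period test, if used: λ = N·(2/3)d²/(1 − ρ), df (2, 92). At the same values: 47 × 0.04 × 0.667/0.7 = 1.790.

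Probability of p < 0.05, versus baseline / joint:

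| d | ρ = 0.3 | ρ = 0.8 |
|---|---|---|
| 0.1 | 0.088 / 0.084 | 0.186 / 0.180 |
| 0.2 | 0.206 / 0.200 | 0.565 / 0.589 |
| 0.3 | 0.398 / 0.406 | 0.889 / 0.921 |

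The joint test is only partly confounded: one of its two degrees of freedom is the counterbalanced active-sham difference and the other is post-stimulation versus baseline. In simulation (400,000 trials per cell) at d = 0.2 with no treatment effect, active minus sham was also significant in 18% of the significant joint tests at ρ = 0.3 and in 8% at ρ = 0.8. With no drift it was about 50%.

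**3. Active minus sham without a period term.** Each participant's difference is τ − π + e (active first) or τ + π + e (sham first), with Var(e) = 2(1 − ρ), where τ is the true effect.
- Leak into the estimate: π(n sham-first − n active-first)/N. At 26/24 this is −2/50 = −4.0% of π. Among the 47, the possible splits run from 26/21 (−5/47 = −10.6%) to 23/24 (+1/47 = +2.1%).
- Type I error (τ = 0, π of 0.2 or 0.3, ρ of 0.3, 0.5 or 0.8, all possible splits; doubly noncentral t integrated numerically): 0.031 to 0.049. The unmodelled period change adds to the residual variance, which makes the test conservative. With a period term it is 0.05.
- Power for τ = 0.5 at ρ = 0.3, with π from −0.3 to +0.3: 0.736 to 0.840 without a period term, against 0.805 to 0.809 with it. Values above 0.81 reflect the leak and are not a real gain.

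**4. Which adjusted model is estimable.**
- Intercept, three-level condition and three-level period: 5 columns, rank 4, so aliased.
- Intercept, active, sham and one indicator for the second post-visit week: 4 columns, rank 4.
- The two post-stimulation weeks only, with condition and period: 3 columns, rank 3.

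**The case against.** A reader might infer that the model lacks the active-sham contrast, or that the stated test cannot answer the hypothesis. The documents do not support that. Active versus sham is among the comparisons listed, and each paragraph of section 9 is headed by its hypothesis, which section 3.1 defines as active relative to sham. The contrast is a coefficient if sham or active is the reference level, and the difference of two coefficients if baseline is.

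A reader might also infer that the missing period term inflates type I error. It does not: the sequences are nearly balanced and the test is, if anything, conservative.

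Nor does any passage say that a joint test was used or that a result against baseline would decide. The larger probabilities need both an assumed drift and a decision rule that the plan does not state. All of this stands, and it limits the point to what section 9 leaves open. It does not remove the point, because section 9 names the comparison for H1a and H2a and leaves it unnamed for H1b and H2b.

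The two participants who "participants completed baseline EMA but lost their phones afterwards, and thus chose not to" complete the later periods are disclosed and carry no within-person information on active minus sham. That discrepancy is minor.

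**Conclusion.** The point holds as a gap in specification. Section 9 does not fix the reference level or the deciding contrast for H1b and H2b, and the alternatives to active minus sham are confounded with time. If one of those alternatives were taken as support, the false-positive probability at an assumed drift of 0.2 SD would be about 0.20 to 0.21 at ρ = 0.3 and 0.565 to 0.589 at ρ = 0.8. These figures illustrate a risk; they do not estimate what happened in this trial.

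For active minus sham itself the harm is small: type I error of about 0.03 to 0.05 for an assumed period change of 0.2 to 0.3 SD, a leak of 4% of the period change at 26/24 and at most 10.6% among the 47, and power as low as 0.74 against 0.81 for an assumed 0.5 SD effect at ρ = 0.3. The change should be made, but the data already held can answer the hypotheses.

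**What to change.** For H1b and for each of the two H2b outcomes, state that EMA-active minus EMA-sham is the sole deciding contrast, adjusted for period (first versus second post-visit week). Either of two models will do:
- fit the two post-stimulation weeks with condition and period; or
- keep baseline in the model and add a single indicator for the second post-visit week.

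Do not add a full three-level period factor, which is aliased with condition. Label comparisons with baseline, and any three-period result, as descriptive. Report how many of the 47 EMA completers were active first and sham first.

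The cost is about one degree of freedom per model and a re-run, with no new data: section 8 already reports compliance by calendar period, so the period index exists. Because the document describes the analyses in the past tense, the re-run should be labelled post hoc.
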